5.2.2. Patient Inclusion Criteria

- Age \geq 21 years
- History of chronic, stable HFrEF with a left ventricular ejection fraction (LVEF) \leq 50%, determined by echocardiography, radionuclide angiography, left ventriculography, or cardiac magnetic resonance imaging, prior to enrollment
- Central sleep apnea, defined using as an apnea-hypopnea index (AHI) $>$ 15/h with \geq 50% central events (apnea and hypopneas)
- New York Heart Association (NYHA) Class III or IV, or NYHA Class II with any of the following:
 - a. at least 1 hospitalization for HF within the 24 months prior to enrollment or
 - b. a BMI corrected BNP \geq 300 pg/ml or a corrected NT-proBNP \geq 1500 pg/ml or
 - c. an ED visit for HF exacerbation where the patient has received an IV diuretic within 12 months of enrollment
- Treatment with stable, optimized GDMT or best tolerated according to applicable guidelines in the U.S. and Canada, where stable is defined as the addition of no new class of disease-modifying drug for \geq 30 days prior to randomization (reasons for intolerance to GDMT must be documented)
- In the investigator's opinion, willing and able to comply with all study requirements
- Able to fully understand study information and sign an IRB-approved informed consent (including HIPAA authorization in the U.S.)

5.2.3. Patient Exclusion Criteria

- Current positive airway pressure use or predominantly obstructive rather than central sleep apnea
- Oxygen saturation $<$ 90% at rest during the day
- Chronic daytime or nighttime use of supplemental oxygen
- Nocturnal oxygen saturation $<$ 88% for $>$ 5 minutes unaccompanied by apneas or hypopneas
- Participants and their bed-partners who currently smoke in the bedroom
- Severe pulmonary disease requiring continuous home oxygen therapy or the continuous or frequent intermittent use of oral steroids or documented severe COPD with FEV1 $<$ 50%

- Cardiac surgery, percutaneous coronary intervention, myocardial infarction or unstable angina within the previous 3 months
- Transient ischemic attack or stroke within the previous 3 months
- Cardiac resynchronization therapy implantation scheduled or performed within 3 months prior to randomization
- Primary hemodynamically-significant uncorrected valvular heart disease (obstructive or regurgitant) or any valvular disease expected to require surgery during the trial
- Acute myocarditis/pericarditis or other cause of potentially reversible cardiomyopathy (e.g., post-partum cardiomyopathy, tachycardia-induced cardiomyopathy), within the previous 6 months
- End-stage (Stage D) HF requiring continuous outpatient intravenous (IV) inotropic therapy, placement of ventricular assist device, listing for cardiac transplantation, or end-of-life care (e.g. hospice care)
- Pregnancy or of child bearing potential without a negative pregnancy test within 10 days prior to enrollment
- Life expectancy < 1 year for diseases unrelated to chronic HF
- Enrolled or planning to enroll in another study that may conflict with protocol requirements or confound subject results in this trial

5.3. Stopping and Discontinuation Criteria

When the study is terminated, the nature of termination will be documented (scheduled end or early discontinuation with justification). Discontinuation of the study will be communicated in writing and will be a decision of the Steering Committee, with input from the NHLBI.

5.3.1. Discontinuation Criteria Related to the Study

Discontinuation of the study may be decided due to efficacy criteria or adverse events in either study group at the discretion of the Steering Committee and the Data and Safety Monitoring Board (DSMB), with input from the NHLBI. The DSMB may recommend early termination of the trial for overwhelming evidence of patient benefit or harm, associated with the intervention. Discontinuation of the study can also be decided if patients cannot be recruited in sufficient numbers within a certain time period (i.e., if enrollment milestones are not substantively met).

5.3.2. Discontinuation Criteria Related to the Patient

The patients will be advised in the informed consent form that they have the right to withdraw from the study at any time without prejudice. In the event that a patient drops out of the study, a study stop form will be completed. In the study stop form, the investigator will record the date and the reason of the individual study termination. The patient will be informed that, in addition to their withdrawal, they can request that none of their data should be analyzed. Otherwise, their data remains in the intention-to-treat group.

Reasonable effort will be made to contact any patient lost to follow up during the course of the study, unless they have withdrawn consent and request that no additional contact be made, in order to complete assessments and retrieve any outstanding data and study supplies.

Once randomized, the patient stays within their group regardless of changes in NOXT treatment, and will be followed to the end of the study. An exception is women who become pregnant during the study, who will be discontinued from the study once pregnancy is identified.

Follow-up will also be stopped (data censored) in patients who reach the endpoints of cardiac transplantation or LVAD implantation. Those patients in whom protocol deviation or violation is noticed will remain in the intention-to-treat group and will be followed according to protocol. If a patient from the control group gets NOXT, they will also remain in the study and will be followed according to protocol.

Patients other than those who experience pregnancy, cardiac transplantation or LVAD implants will be followed according to the study protocol, regardless of whether they experience a primary endpoint. This will allow for recurrent event analyses.

Study therapy may be stopped in several circumstances: a) by participant request; b) if the participant's clinical situation changes and his provider prescribes oxygen therapy indefinitely or other therapy that precludes use of oxygen; or c) the participants become pregnant, undergoes cardiac transplantation or LVAD implant. All attempts will be made to continue outcomes assessments on these patients.

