	
Quality of Life and Symptoms
 
 • Change in HF disease-specific quality of life, assessed by Kansas City Cardiomyopathy Questionnaire (KCCQ) • Change in generic-quality of life, assessed by the EQ-5D • Change in depressive symptoms assessed by the PHQ-8 • Change in sleep symptoms and sleep related daytime impairment (including fatigue), assessed by the PROMIS Sleep Disturbance and Sleep Related Impairment Questionnaires 
Functional Status
 
 • Change in NYHA Functional Class Ranking 
Secondary morbidity and mortality endpoints will be measured over the full duration of study follow up. Quality of life, symptoms, and functional status endpoints will be measured at baseline and at 6 and 12 months follow up.

Safety Assessments	Continuous assessment of study-related adverse events (AEs) will be collected.
Scheduled follow up	
Patients will be followed up on average for a period of about 2.5 years. All patients will be followed, until the last patient randomized completes 6 months of follow up. Thus, minimum follow up time will be 6 months, and maximum follow up is anticipated to be about 4.5 years, assuming that the enrolment accrual pattern is uniform across and completed over 3.5 years.
 
In-clinic or remote study visits will occur at Screening/Consent, Baseline, 6 months, and 12 months. Telephone follow-up will occur at 1 month, 3 months, 9 months, 18 months, and then every 6 months after that, until the last participant completes the study. There will be a telephone assessment for each patient at the end of the study, for final ascertainment of mortal and morbid events.
 
Prior the De-briefing Visit, a follow-up in home sleep study will be performed. At the De-briefing Visit the coordinator will review the baseline and follow-up sleep study results, reveal the participant's treatment arm and provide letters for continuity of care.

Independent Committees	
An independent CEC will adjudicate all outcomes associated with the primary and secondary mortality and morbidity endpoints.
 
An Independent Data and Safety Monitoring Board (DSMB) will monitor all efficacy and safety outcomes (including study-related AEs), but will be able to recommend early termination of the trial only for significant excess mortality in the treatment group or for overwhelming evidence of patient benefit or harm.

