8.2. Follow Up and Procedures during the Study Visits/Calls

In-clinic study or remote visits will occur at Screening/Consent, Baseline, 6 months, and 12 months. Telephone follow-up will occur at 1 month, 3 months, 9 months, and 18 months, and then every 6 months after that, until the last participant completes the study. There will be a telephone assessment for each patient at the end of the study, for final ascertainment of mortal and morbid events. Patients potentially meeting eligibility criteria will be consented for further screening. There are two pathways for determination of CSA eligibility for the LOFT-HF trial: a clinical sleep study, polysomnography or home sleep apnea test within 12 months prior to randomization; or a research polysomnogram obtained at home or prior to hospital discharge, when the participant is considered at a baseline, stable condition. The research PSG device is designed for unattended sleep monitoring and contains high quality sensors for quantifying ventilation and oxygenation, and has the ability to measure EEG using self-applied sensors.

Participants will be instructed on how to apply several simple electrodes at home before bed, and return the devices by courier, mail, or direct pick up or drop off. For studies done in the in-patient setting, sensors will be applied by research personnel.

After the results of the clinically-obtained or research PSG are obtained and centrally scored by the SRC, patients meeting sleep eligibility criteria will be invited to participate in a brief baseline examination (remote or in-person) which will include administration of questionnaires (patient-reported outcomes). At the end of the visit, patients will be randomized (stratified by center and the presence or absence of high-risk markers) to sham oxygen (control group) or to NOXT (treatment group). All participants will receive standardized sleep education. A Philips-Respirronics EverFlo stationary concentrator for in-home use will be provided to each participant. Devices will be delivered and installed and patients educated on their use by study staff and/or vendors with established agreements with the study (through a DME company, similar to the INOX trial [<https://clinicaltrials.gov; NCT01044628>]).

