8.7.2. Life-saving Cardiovascular Interventions

Life-saving CV interventions will be identified using criteria that are considered as being equivalent to HF-related death (i.e., progressive pump dysfunction or sudden [arrhythmic] cardiac death), including cardiac transplantation, long-term ventricular assist device implantation, resuscitation of sudden cardiac arrest, or shock from an implantable cardioverter-defibrillator (ICD) associated with sudden loss of consciousness associated with ventricular tachycardia or ventricular fibrillation.

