11.2. Statistical Analysis Approaches

Primary analyses will follow the “intention-to-treat” principle; that is, individuals will be analyzed according to their assigned treatment group, whether or not they receive the study treatment as assigned. Every effort will be made to obtain follow-up data on all randomized subjects, whether or not they follow their assigned treatment. Preliminary Analyses

Our approach will involve close collaboration between clinical experts (on the Steering Committee and Scientific Advisory Committee) and biostatisticians, while ensuring appropriate blinding. Interim analyses of baseline variables (aggregated across intervention groups) will be conducted early in the study to ensure that the collected and derived data follow the assumed distributions, and that appropriate methods for identifying outliers and for computing clinical scores are implemented. Reports will provide a full description of the distributions of each study variable, along with indices of associated data quality, and include graphical displays. The amount and patterns of missing data, if any, will be characterized. Measures that are not normally distributed may be transformed to meet model assumptions. Before conducting final analyses, descriptive statistics will be generated using the total data set, ensuring that outliers or potential discrepancies in the data are resolved.

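### Section 5.3.2 both stops and continues outcome follow-up after cardiac transplantation, LVAD or pregnancy; if its censoring rule is applied, deaths after transplant or LVAD drop out of the standalone mortality endpoints

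*Combined protocol and SAP*

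**What the plan says.** The conflict lies within Section 5.3.2 (Discontinuation Criteria Related to the Patient).

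- On transplant and LVAD: "Follow-up will also be stopped (data censored) in patients who reach the endpoints of cardiac transplantation or LVAD implantation".
- On pregnancy: "An exception is women who become pregnant during the study, who will be discontinued from the study once pregnancy is identified".
- On all three groups: "Patients other than those who experience pregnancy, cardiac transplantation or LVAD implants will be followed according to the study protocol". The next sentence gives the recurrent-event analyses as the reason for following everyone else.
- The closing paragraph lists the circumstances in which study therapy may stop. Item c is pregnancy, transplantation or LVAD. It ends: "All attempts will be made to continue outcomes assessments on these patients".

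Elsewhere, Section 8.2 says: "There will be a telephone assessment for each patient at the end of the study, for final ascertainment of mortal and morbid events". The synopsis and Section 4.3 say: "All patients will be followed, until the last patient randomized completes 6 months of follow up". Section 11.2 says: "Every effort will be made to obtain follow-up data on all randomized subjects".

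Section 3.1.2 lists all-cause mortality and CV mortality as separate secondary endpoints, with recurrent-event analyses of two composites and of HF hospitalisation. Section 8.7.2 identifies transplant and long-term VAD by "criteria that are considered as being equivalent to HF-related death". In Section 11.2.3 the only competing event named is death from other causes.

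**The concern.** One sentence ends observation at transplant or LVAD and another continues it for the same patients. A site could follow either, and data not collected cannot be recovered by a later analysis decision.

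If observation ends, deaths after the procedure leave the standalone mortality endpoints. By the protocol's own description these patients have reached something close to HF death, so the censoring is linked to prognosis. If oxygen changes the rate of transplant or LVAD, the arms lose deaths unequally.

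The affected analyses are secondary, and Section 11.2.3 calls them exploratory. The synopsis, however, names excess mortality on active treatment as a ground on which the DSMB may recommend stopping, so the death count needs one definition.

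**Working it through.** **1. Do the sentences conflict?** The closing promise covers the circumstances listed just before it, and item c names transplant, LVAD and pregnancy. Reading that paragraph as concerning therapy only does not remove the conflict: it says therapy may stop while outcome assessment goes on, whereas the earlier sentences stop follow-up itself. Section 8.2 (a final call for each patient) supports continued ascertainment. The synopsis, Section 4.3 and Section 11.2 are general statements with which a specific exception could coexist. The contradiction therefore rests on Section 5.3.2.

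**2. Which analyses are exposed if the rule is applied?**

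| Analysis | Effect of censoring at transplant/LVAD |
|---|---|
| Primary composite, time to first event | None; the procedure is already an event |
| Time-to-first composites that count life-saving CV interventions | None |
| All-cause mortality; CV mortality | Later deaths lost |
| Recurrent-event composites; HF hospitalisation rate | Later hospitalisations lost; later deaths also lost from the composites |
| First HF hospitalisation (Section 11.2.3) | Lost if it follows the procedure |

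Pregnancy is not an endpoint. Stopping follow-up there could remove later primary events, probably very few.

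**3. How many deaths?** There is no figure in the plan to reproduce. The documents give 858 patients and a mean follow-up of 2.49 years (Section 11.2.5). All rates below are assumptions, used as constant hazards per year with no treatment effect: procedure p = 1, 3, 5%; death without procedure d = 8, 12, 15%; death after procedure q = 10, 20, 30, 40%. Follow-up T is taken as uniform from 0.5 to 4.48 years, so the mean is (0.5 + 4.48)/2 = 2.49.

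Per patient, with k = p + d:

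- procedures = (p/k)(1 − e^(−kT))
- deaths without procedure = (d/k)(1 − e^(−kT))
- alive after procedure = p(e^(−kT) − e^(−qT))/(q − k)
- deaths after procedure = procedures − alive after procedure

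Averaged over T and multiplied by 858:

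| p, d, q | Procedures | Deaths after procedure | All deaths | Share lost |
|---|---|---|---|---|
| 1%, 15%, 10% | 17.0 | 2.4 | 257.6 | 0.9% |
| 3%, 12%, 20% | 51.7 | 13.3 | 220.2 | 6.0% |
| 5%, 8%, 40% | 88.6 | 37.4 | 179.2 | 20.9% |

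Over the whole grid there are 17 to 89 procedures, 2.4 to 37.4 deaths after a procedure, and 152 to 277 deaths in all.

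Section 8.3 has follow-up stopping on Dec 15 2021. With first enrolment in May 2019 (Section 10.4.1) and accrual on the Section 10.4.2 milestones, about 294 to 401 patients would contribute. The same formulas then give about 3 to 21 procedures and about 0.3 to 5.5 later deaths, of roughly 29 to 64 in all.

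**4. How far would the mortality hazard ratio move?** This compares the Cox hazard ratio for death with censoring at the procedure against the one using all deaths. It applies to full-plan follow-up only, with d = 8 or 15% and q = 10, 20 or 40%. The effect sizes are assumptions; 0.755 is the plan's primary hazard ratio, borrowed for procedures.

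| Assumed effect of oxygen | Largest shift at p = 1% / 3% / 5% |
|---|---|
| Procedure HR 0.755; death HR 0.8 before and after procedure | 0.007 / 0.019 / 0.028 |
| Same, no effect on death after procedure | 0.0025 / 0.007 / 0.012 |
| On procedures only | 0.010 / 0.027 / 0.041 |
| On deaths without procedure only | 0.010 / 0.026 / 0.040 |
| Opposed: procedure HR 1.325, death HR 0.8 throughout | 0.013 / 0.034 / 0.052 |
| Opposed, no effect on death after procedure | 0.023 / 0.062 / 0.095 |

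The direction can go either way. In the first row the median shift is 0.002, 0.006 and 0.009 at p = 1, 3 and 5%. In the last row only 5 of the 18 combinations (28%) stay within 0.01.

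For scale, take the worst cell. The censored hazard ratio is 0.80 by construction and the all-deaths one is about 0.894, so ln(0.894/0.80) = 0.111. The standard error with about 179 deaths is roughly 2/√179 = 0.149, so the shift is 0.111/0.149 = 0.74 of a standard error.

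The loss from the recurrent-event analyses cannot be sized, because no rate of later hospitalisation is given.

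**The case against.** The strongest case against is that Section 5.3.2 leans towards stopping. Two of its three statements on transplant and LVAD stop follow-up or exempt these patients, and the second ties the recurrent-event analyses to everyone else. Ending observation at an event regarded as equivalent to HF death is a recognisable choice. Section 3.1.2 already has companion endpoints, all-cause or CV mortality combined with life-saving interventions, which count these procedures and so avoid this censoring. Procedures may be few, since Section 5.2.3 excludes patients who are listed for transplant or have a VAD placed. The separate SAP cited in Section 11.2.4, the Manual of Procedures or the CEC manual may settle the matter.

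Much of this stands. For the recurrent-event analyses the exclusion may be deliberate, so what is needed there is a stated rule. The companion composites do limit the damage, but they do not repair standalone mortality. An unseen SAP rule could settle the analysis, but Section 5.3.2 would still contradict itself on whom sites keep following.

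Three stronger readings are tempting, and the documents support none of them:

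- A reader might infer that the primary analysis is biased. For transplant and LVAD it is not, because the event has already been counted.
- A reader might infer that the interim efficacy boundary is affected, because Section 11.2.5 words it in terms of mortality and HF hospitalisation rates. That section opens by saying that the primary outcome is monitored, and the wording can be read as that composite.
- A reader might infer that these deaths will be lost, or that sites are already acting differently. The closing sentence promises the opposite, and site practice cannot be seen.

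**Conclusion.** The contradiction is certain; its consequence depends on which sentence is applied. If the censoring rule governs, standalone all-cause and CV mortality lose every death after transplant or LVAD, in a way linked to prognosis.

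The effect is probably small. It is often within 0.01 on the mortality hazard ratio under full-plan follow-up. Where the assumed effects on procedures and deaths are not opposed, the largest shift is about 0.03 at 3% procedures a year and about 0.04 at 5%. Where they are opposed, it reaches about 0.06 at 3% and 0.10 at 5%, in each case with 40% yearly mortality after the procedure. These sizes rest wholly on assumed rates and constant hazards.

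The point should be corrected because mortality is a safety criterion and uncollected data are not recoverable. It does not threaten the primary result.

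**What to change.** - Reconcile the sentences in Section 5.3.2 so that stopping study therapy is separate from stopping outcome ascertainment. This concerns ascertainment and analysis only, not when therapy stops.
- Continue vital-status and endpoint ascertainment to study close, through the calls already in Sections 8.2 and 8.4, for every randomised patient who has not withdrawn consent to contact. This includes patients with transplant, LVAD or pregnancy.
- Analyse standalone all-cause and CV mortality on all ascertained deaths. A sensitivity analysis censoring at transplant or LVAD is optional.
- State whether events after transplant or LVAD count in the recurrent-event and first-HF-hospitalisation analyses. Leave the composites as they are.
- Make Section 5.3.2 agree with any censoring rule in the separate SAP.

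The cost is a wording change, a few more calls (for about 17 to 89 transplant or LVAD patients under the full plan, about 3 to 21 if follow-up stops on Dec 15 2021, on the assumed rates) and slight extra analysis work.

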5.4. Randomization

Patients meeting all of the inclusion and none of the exclusion criteria will be randomized to one of two groups, a control group receiving optimal GDMT and sham NOXT and a treatment group receiving optimal GDMT and active NOXT.

Patients will be randomly assigned to one of the two study groups in a 1:1 ratio using a permuted block design, stratified by the presence or absence of high-risk markers (hospitalization for HF in the last 12 months and/or an elevated outpatient BNP or NTproBNP level), within sites. Eligible participants will be randomized via a web-based randomization module, initiated by the research coordinator at the participating clinical center. The data management system will confirm all eligibility criteria, and will deliver a randomization identifier (e.g., A or B). Randomization codes also will be linked to identifiers of each oxygen concentrator, providing the ability to assign a participant a concentrator without unblinding local staff. The randomization distributions and system will be re-assessed on a quarterly basis to ensure that it is working as expected. To minimize problems with connectivity, staff will be asked to confirm Internet connectivity at the beginning of the baseline visit to avoid any problems with entry of the randomization case report form. If problems arise with connectivity during a given baseline visit, site staff will be asked to immediately contact the Data Coordinating Center to resolve these; a manually generated randomization assignment would then be generated based upon the subject stratification factor.

6. Investigational Intervention

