6.1. General Approach

All patients (treatment and control) will receive standardized sleep education addressing sleep hygiene recommendations that provide guidance on regular bed and wake times; avoidance of alcohol, caffeine, and excessive fluid and food consumption before bedtime; sleeping in dark, cool, and quiet quarters; use of the bed for sleep and intimacy only; avoidance of excessive napping; and avoidance of TV or light exposure before bedtime.

At the end of the baseline visit, after randomization, arrangements will be made to provide each participant a Philips-Respirronics Everflo stationary unit concentrator (active or sham) for in-home use, with optional humidification. This may be through a DME or other local resources. Each unit will contain Bluetooth central monitoring capacity, providing ongoing real-time use

monitoring (indications of flow rates and flow rate changes). The sham model delivers pressurized room air, providing the same sounds and appearances as the active device. Inventories for each device (serial numbers, sham versus active) will be monitored at SRC, and the SRC will instruct the local staff/DME provider as to which specific concentrator (serial number to use).

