8.3. Follow-up Sleep Study and De-briefing Visit

Before the De-briefing Visit, participants will undergo a repeat in-home sleep assessment to serve two purposes: a) provide critical clinical data for use in transitioning to routine clinic care; and b) to maximize the scientific impact of the LOFT-HF study. Participants will be contacted by phone, mail, and/or in-person (coordinating with regularly scheduled clinic or research visits) and offered the opportunity to undergo a repeat in-home research sleep study. The equipment and procedures are the same as described for the research sleep screening visit other than participants will be asked to use their assigned LOFT-HF study treatment during the study and not use the nasal pressure cannula. (The two cannot easily be used together). Devices and equipment will be distributed and returned in-person, by courier, or mail. Study data will be analysed by the BWH SRC, and reports generated with summary data from the overnight sleep study.

At the time of the De-briefing Visit, held on or after Dec 15 2021, when study follow-up will stop, the coordinator will complete assessments for study intervention (sham/NOXT) adherence; collect any pending research data not previously collected (e.g., missing questionnaires); assess for new AEs that occurred up until the final study follow-up date; determine if any medication changes have occurred since last contact thought Dec 15 2021; determine if any clinical outcomes events have occurred through Dec 15 2021; and complete a general rating of improvement/satisfaction survey. After these data are collected, Participants will be provided with a letter that informs the participant of which arm they were randomized to and the results of the baseline and follow-up sleep studies. Participants will be encouraged to discuss further clinical management with their physicians; if needed, the participant will be provided a list of local sleep specialists to access for further clinical follow-up. The coordinator will arrange for return of the oxygen concentrator for final equipment disposition, and if requested, provide a letter to the PCP for continuity of care.

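### Section 5.4 gives the randomisation identifier as a letter such as A or B; if sites see it and it tracks the arm, the first arm revealed at de-briefing decodes a site's other patients before their final data are in

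*Combined protocol and SAP*

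**What the plan says.** Section 5.4 (Randomization) allocates 1:1 "using a permuted block design, stratified by the presence or absence of high-risk markers", within sites; no block size is given. The module is "initiated by the research coordinator at the participating clinical center". After checking eligibility, the data management system "will deliver a randomization identifier (e.g., A or B"). The section then says that randomisation codes are also linked to concentrator identifiers, "providing the ability to assign a participant a concentrator without unblinding local staff".

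Section 6.1 (General Approach) describes dispensing. The Sleep Reading Center (SRC) keeps the inventory of active and sham serial numbers, and "the SRC will instruct the local staff/DME provider as to which specific concentrator" to use.

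The Synopsis (Scheduled follow up) has the coordinator, at the De-briefing Visit, reveal the participant's "treatment arm and provide letters for continuity of care". Section 8.3 sets the order within that visit. Adherence, missing data, new adverse events, medication changes, outcome events through 15 December 2021 and a satisfaction survey come first. The participant then receives a letter that "informs the participant of which arm they were randomized to". Visits take place on or after 15 December 2021. Section 8.4 places them within six weeks of the last randomised participant's 6-month visit.

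Section 13 adds that data access depends on each person's blinded or unblinded role, and that filtering lowers the chance of unblinding. It does not mention the randomisation identifier.

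**The concern.** The trial depends on a double-blind sham. With a label shared by everyone in an arm, patients' blinds are not independent of one another: learning one patient's arm gives the key to all patients carrying either letter. With an identifier unique to each patient, learning one arm reveals one arm.

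This would matter less if no arm were revealed until a site had finished collecting data. Section 8.3 protects each patient's own data by collecting them before that patient's letter. It does not protect the next patient on the list. A coordinator who has delivered one letter and can look up the A/B codes would know the arms of patients still to be asked about events, adverse events and satisfaction. Under Section 7.2 the site investigator adjudicates adverse events, and their relatedness to the intervention is recorded, so the knowledge could reach that judgement too.

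**Working it through.** The plan states no figure on this point, so there is none to reproduce. The check sets the sections side by side and then counts the patients exposed.

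**1. Is the identifier an arm label?** Its only specification is a two-valued example in a two-arm, 1:1 trial. Decoding needs two further conditions: the letter is visible at the site, and one letter means one arm there. Section 5.4 states neither. No section says that the letter is hidden, unique to a patient, or re-keyed between patients, strata or sites.

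**2. Does the site need it?** No. Under Section 6.1 the site or equipment supplier is told a serial number, which is enough to dispense the device.

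**3. Is there a documented disclosure while data are outstanding?** Yes. The Synopsis and Section 8.3 have the coordinator reveal arms one participant at a time, and Section 8.4 spreads the visits over weeks. No section makes a site's first letter wait for its last data collection.

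**4. How many patients does a first disclosure expose?**

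- Last randomisation: de-briefing opens on 15 December 2021 and minimum follow-up is 6 months (Section 4.3), which puts it at about mid-June 2021.
- Enrolment by then: Section 10.4.2 expects 215 in January 2021 and 429 in January 2022. Linear interpolation over 5 of 12 months gives 215 + (5/12) × (429 − 215) = 215 + 89 = 304, or roughly 300.
- Sites: 30 to 50 (Synopsis).

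| Enrolled | 50 sites | 30 sites | Others exposed at first disclosure |
|---|---|---|---|
| about 300 (mid-2021) | 300/50 = 6 | 300/30 = 10 | about 5 to 9 |
| 215 (January 2021 milestone) | 4.3 | 7.2 | about 3 to 6 |
| 429 (January 2022 milestone) | 8.6 | 14.3 | about 8 to 13 |
| 858 (full enrolment) | 17.2 | 28.6 | about 16 to 28 |

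The first row fits a December 2021 close, and the next two bracket it. The last row would apply only if the trial reached 858. All are averages over sites. Each is the most that a single disclosure exposes, and the number falls as further visits are completed. With patient-unique identifiers and no shared letter, a disclosure reveals one patient directly.

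**5. Which data are still open?** Section 8.3 lists outcome events up to the cut-off, new adverse events, missing questionnaires and the satisfaction survey. NYHA class and the scheduled questionnaires are due at 6 and 12 months (Section 8.4), so only catch-up questionnaires are affected.

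**The case against.** The strongest reply is that the protocol never says what the concern needs. The letters are introduced as an example, the sentence names no recipient, and the next one gives the aim of keeping local staff blinded. With the SRC holding the device inventory and role-based data access, the text fits a code that stays behind the blind. This stands as far as it goes: a reader might infer that sites are certainly handed an arm code, and the documents do not establish that. But the only specification given is a two-valued label from a module that the site runs, and no safeguard named for it rules out the problem.

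A second reply is that follow-up has stopped before any letter is given, so disclosure cannot change whether events occurred. That is right. It can still affect which late events are reported and how they are described. The Clinical Endpoints Committee (CEC) adjudicates blinded, with two physician reviewers, and can identify events itself (Sections 13 and 14.1.2). This limits the effect on the primary endpoint but does not remove it, because the committee works from documents that sites send. Adverse events and surveys do not have this protection.

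Other unblinding routes are tempting to add. A provider's oxygen prescription (Section 5.3.2) is not shown to reveal the study arm, and no section describes an oxygen reading at the device. A staff guess decodes a site only if it is right. None of these is relied on here.

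**Conclusion.** The point holds conditionally. If the Section 5.4 letter is visible to the site and keyed constantly to arm, the disclosure order in Section 8.3 lets the first de-briefed patient unblind about 5 to 9 others at an average site while their final data are outstanding. This rests on those two conditions, on interpolating the plan's enrolment milestones, and on 30 to 50 sites of average size.

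The data affected are late event reports, adverse event relatedness, outstanding questionnaires and the satisfaction survey, which is not a listed endpoint.

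Three stronger conclusions do not follow. One is that a single disclosure decodes all 858 patients: this would need a trial-wide key, which is not stated, and full enrolment, which does not fit the December 2021 close. Another is that NYHA class and quality-of-life results are generally compromised: their scheduled assessments are at 6 and 12 months, not at de-briefing. The third is that allocation concealment fails during enrolment: the one documented disclosure comes after enrolment has ended. No sample size or power figure changes. The revision is worth making because the exposure is avoidable at low cost.

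**What to change.** - **Section 5.4:** state that sites see only a patient-unique identifier or the concentrator serial number, and that arm codes are held at the Data Coordinating Center and the SRC.
- **Section 8.3, with matching text in the Synopsis and Section 8.4:** release arm letters at a site only once final outcome, adverse event and survey data have been collected for all its participants. Add a time limit so that letters are not held indefinitely when a participant cannot be reached.

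The cost is wording, a system configuration check and a short wait for some participants' letters. The wait matters because the visit also serves the transition to routine care, hence the time limit.

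The Section 5.4 change cannot recall identifiers already issued. The protocol version is dated 15 May 2021, so about a month of randomisation would remain before a mid-June close, and most of the protection would come from the Section 8.3 change. Some inference from the permuted blocks remains once arms are disclosed, whatever identifier is used; the sequencing rule puts that inference after the site's own data collection.
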